## DOCUMENT HISTORY

Document	Date of Issue	Overall Rationale
Amendment 3	01-JUL-2022	Merck Sharp & Dohme Corp. underwent an entity name and address change to Merck Sharp & Dohme LLC, Rahway, NJ, USA. This conversion resulted only in an entity name change and update to the address.
Amendment 2	08-JUN-2021	To harmonize the presentation of safety information across all FDA-approved PD-1/L1 antibody prescribing information and to update imaging frequency.
Amendment 1	25-SEP-2020	Country-specific change, procedural updates, clarification of ORR, and removal of substudy references for Future Biomedical Research.
Original Protocol	25-SEP-2018	Not applicable

## PROTOCOL AMENDMENT SUMMARY OF CHANGES

**Amendment: 03**

### Overall Rationale for the Amendments:

Sponsor underwent an entity name change and update to the address.

### Summary of Changes Table:

Section # and Name	Description of Change	Brief Rationale
Title Page Section 10.1.1 Code of Conduct for Clinical Trials Throughout	Sponsor entity name and address change.	Merck Sharp & Dohme Corp. underwent an entity name and address change to Merck Sharp & Dohme LLC, Rahway, NJ, USA. This conversion resulted only in an entity name change and update to the address.

## 1 PROTOCOL SUMMARY

### 1.1 Synopsis

**Protocol Title:** A Phase 3 Open-label, Single Arm Study to Evaluate the Safety and Efficacy of Pembrolizumab (MK-3475) as First-line Therapy in Participants With Advanced Merkel Cell Carcinoma (KEYNOTE-913)

**Short Title:** Pembrolizumab (MK-3475) as First-line Therapy for Advanced Merkel Cell Carcinoma

**Acronym:** KEYNOTE-913

#### Hypotheses, Objectives, and Endpoints:

There are no hypotheses for this study.

In participants at least 12 years of age with advanced Merkel cell carcinoma (MCC):

Primary Objectives	Primary Endpoints
- Objective: To assess the objective response rate (ORR), as assessed by blinded independent central review (BICR) per Response Evaluation Criteria in Solid Tumors version 1.1 (RECIST 1.1) modified to follow a maximum of 10 target lesions and a maximum of 5 target lesions per organ, following administration of pembrolizumab	- Objective response (OR): Complete response (CR) or partial response (PR)
Secondary Objectives	Secondary Endpoints
- Objective: To assess duration of response (DOR), as assessed by BICR per RECIST 1.1 modified to follow a maximum of 10 target lesions and a maximum of 5 target lesions per organ, following administration of pembrolizumab	- DOR: For participants who demonstrate confirmed CR or PR, the time from first documented evidence of CR or PR until disease progression or death from any cause, whichever occurs first
- Objective: To assess the progression-free survival (PFS), as assessed by BICR per RECIST 1.1 modified to follow a maximum of 10 target lesions and a maximum of 5 target lesions per organ, following administration of pembrolizumab	- PFS: The time from the first day of study treatment to the first documented disease progression per RECIST 1.1 by BICR or death due to any cause, whichever occurs first

- Objective: To assess overall survival (OS) following administration of pembrolizumab	- OS: The time from the first day of study treatment to death due to any cause
- Objective: To assess safety and tolerability of treatment with pembrolizumab	- Adverse events (AEs)

**Overall Design:**

Study Phase	Phase 3
Primary Purpose	Treatment
Indication	Treatment of unresectable Stage III and Stage IV MCC
Population	Participants with no prior systemic therapy for advanced MCC (prior adjuvant therapy is permitted)
Study Type	Interventional
Intervention Model	Single Group This is a multi-site study
Type of Control	No Treatment Control
Study Blinding	Unblinded Open-label
Masking	No Masking
Estimated Duration of Study	The Sponsor estimates that the study will require approximately 13 years from the time the first participant signs the informed consent/assent until the last participant's last study-related telephone call or visit.

**Number of Participants:**

Approximately 50 participants will be allocated to study intervention.

**Intervention Groups and Duration:**

Intervention Groups	Intervention Group Name	Drug	Dose Strength	Dose Frequency	Route of Admin.	Regimen/ Treatment Period	Use
		Pembrolizumab	Pembrolizumab (MK-3475)	200 mg (adult participants) or 2 mg/kg (up to 200 mg; pediatric participants) on Day 1 of each cycle	Q3W	IV	Up to 35 administrations (approximately 2 years)
IV=intravenous; Q3W=every 3 weeks							
Total Number	1 intervention group						
Duration of Participation	
Each participant will participate in the study from the time the participant provides documented informed consent through the final protocol-specified contact.
 
After a screening phase of up to 28 days, each participant will be assigned to receive study intervention until disease progression is radiographically documented, confirmed by the site per modified Response Evaluation Criteria in Solid Tumors 1.1 for immune-based therapeutics (iRECIST) when clinically appropriate, unacceptable adverse event(s) (AEs), pregnancy, intercurrent illness that prevents further administration of treatment, investigator’s decision to discontinue the participant, administrative reasons requiring cessation of treatment, or until the participant has received 35 administrations of pembrolizumab (approximately 2 years).
 
After the end of treatment, each participant will be followed for the occurrence of AEs and spontaneously reported pregnancy as described under Section 8.4.
 
Participants who discontinue for reasons other than radiographic disease progression will have post-treatment follow-up imaging for disease status until disease progression is documented radiographically per RECIST 1.1, and when clinically appropriate, confirmed by the site per iRECIST, the start of a new anticancer treatment, withdrawal of consent, pregnancy, death, or loss to follow-up. All participants will be followed by telephone for overall survival until death, withdrawal of consent, or the end of the study.
 
Once the participant has achieved the study objective or the study has ended, the participant is discontinued from this study and will be enrolled in an extension study to continue protocol-defined assessments and treatment.
						

**Study Governance Committees:**

Steering Committee	No
Executive Oversight Committee	No
Data Monitoring Committee	No
Clinical Adjudication Committee	No
Study governance considerations are outlined in Appendix 1.	

[figure not shown]
**Study Accepts Healthy Volunteers:** No

A list of abbreviations used in this document can be found in Appendix 10.

**1.2 Schema**

The study design is depicted in [Figure 1](#).

Figure 1 KEYNOTE-913 Study Design

BICR=blinded independent central review; C1D1=Cycle 1 Day 1; DOR=duration of response; ORR=objective response rate; OS=overall survival; PFS=progression-free survival; Q3W=every 3 weeks; Q12W=every 12 weeks; Q24W=every 24 weeks; RECIST=Response Evaluation Criteria In Solid Tumors

- a Prior adjuvant therapy may be allowed as detailed in Section 5.1, inclusion criterion #2.
- b Imaging to be performed Q12W or sooner if clinically indicated after C1D1 ( $\pm 7$  days) until Week 54 of study intervention, Q24W thereafter or sooner if clinically indicated, or more frequently if required by local standard of care, until disease progression per RECIST 1.1.
- c If End of Treatment visit occurs >30 days after last dose of study intervention, a Safety Follow-up Visit is not required.
- d For participants discontinuing for reasons other than disease progression, tumor imaging should continue to be performed as if on study intervention (ie, Q12W until Week 54 after C1D1 ( $\pm 7$  days), Q24W thereafter or sooner if clinically indicated, or more frequently if required by local standard of care, until disease progression per RECIST 1.1).
- e Participants in Survival Follow-up will be contacted approximately Q12W or sooner to assess for survival status or death, withdrawal of consent, or the end of study, whichever occurs first.

### 1.3 Schedule of Activities (SoA)

Procedures and activities are outlined in [Table 1](#).

Table 1 Study Schedule of Activities

Study Period	Screening Phase	Intervention Phase (Q3W)			End of Treatment	Post-treatment Follow-up			Notes
		1	2	3 and onwards		Safety Follow-up a	Follow-up b	Survival Follow-up	
Treatment Cycle					Discontinuation				Procedures should occur predose on Day 1 of each cycle unless otherwise noted.  Post-treatment Period: Refer to Section 8.12.3.
Scheduled Timing	-28 to -1				At time of d/c	30 days post last dose		~Q12W (telephone)	
Window (days):		+ 3	± 3	± 3		+ 7	± 7	± 7	
Administrative Procedures									
Informed Consent/Assent	X								Consent/assent form can be signed at any time prior to any protocol-specific screening procedures being performed. Additional consent/assent is required at disease progression.
Informed Consent/Assent for Future Biomedical Research	X								Participation in future biomedical research is not mandatory for participation in this study.
Inclusion/Exclusion Criteria	X								
Participant Identification Card	X								
Medical/Surgical History and Demographics	X								Significant medical/surgical history will be captured for last 10 years.
Staging	X								At initial diagnosis and at study entry.

Study Period	Screening Phase	Intervention Phase (Q3W)			End of Treatment	Post-treatment Follow-up			Notes
		1	2	3 and onwards		Safety Follow-up a	Follow-up b	Survival Follow-up	
Treatment Cycle					Discontinuation				Procedures should occur predose on Day 1 of each cycle unless otherwise noted.  Post-treatment Period: Refer to Section 8.12.3.
Scheduled Timing	-28 to -1				At time of d/c	30 days post last dose		~Q12W (telephone)	
Window (days):		+ 3	± 3	± 3		+ 7	± 7	± 7	
Prior and Concomitant Medication Review	X	X	X	X	X	X	X		Record all prior medications taken within 28 days before C1D1. Enter new medications started during the study through the post-treatment Safety Follow-up. Record concomitant medications beyond 30 days after treatment discontinuation if related to SAE or ECI.
Study Intervention									
Intervention Allocation		X							Participants will be allocated on C1D1 (-3 days) after confirmation of eligibility.
Pembrolizumab (MK-3475) Administration		X	X	X					Pembrolizumab 200 mg Q3W for adult participants or 2 mg/kg (up to 200 mg) Q3W for pediatric participants.
Poststudy Anticancer Therapy						X	X	X	All anticancer therapy will be recorded until time of death or termination of Survival Follow-up. If a clinic visit is not feasible, follow-up information may be obtained via telephone or e-mail.

Study Period	Screening Phase	Intervention Phase (Q3W)			End of Treatment	Post-treatment Follow-up			Notes
		1	2	3 and onwards		Safety Follow-up a	Follow-up b	Survival Follow-up	
Treatment Cycle					Discontinuation				Procedures should occur predose on Day 1 of each cycle unless otherwise noted.  Post-treatment Period: Refer to Section 8.12.3.
Scheduled Timing	-28 to -1				At time of d/c	30 days post last dose		~Q12W (telephone)	
Window (days):		+ 3	± 3	± 3		+ 7	± 7	± 7	
Survival Status		<----->						X	After investigator-determined PD or start of new anticancer treatment. In addition, upon Sponsor request, participants may be contacted for survival status at any time during the course of the study (unless this information is not allowed to be provided due to confidentiality).
Efficacy Procedures									
Tumor Imaging (CT/MRI; Chest, Abdomen, and Pelvis)	X	<-----> c			X d			X	Prior scans performed within the screening period but before signing informed consent may be used if consistent with protocol requirements per SIM. All imaging visits have a scheduling window of ±7 days. Imaging to be performed Q12W or sooner if clinically indicated from the date of C1D1 until Week 54 of study treatment, Q24W or sooner if clinically indicated thereafter, or more frequently if required by local standard of care until disease progression per RECIST 1.1.

Study Period	Screening Phase	Intervention Phase (Q3W)			End of Treatment	Post-treatment Follow-up			Notes
		1	2	3 and onwards		Safety Follow-up a	Follow-up b	Survival Follow-up	
Treatment Cycle					Discontinuation				Procedures should occur predose on Day 1 of each cycle unless otherwise noted.  Post-treatment Period: Refer to Section 8.12.3.
Scheduled Timing	-28 to -1				At time of d/c	30 days post last dose		~Q12W (telephone)	
Window (days):		+ 3	± 3	± 3		+ 7	± 7	± 7	
Safety Procedures									
Height	X	X	X	X	X				Pediatric height to be measured at every visit. Adult height measured at Screening only.
Weight	X	X	X	X	X				To be measured at every visit.
Full Physical Examination	X								Within 7 days prior to C1D1.
Directed Physical Examination		X	X	X		X			A symptom-directed physical examination may be performed at any time during the study, as clinically indicated.
Vital Signs (resting BP, pulse rate, respiratory rate, temperature)	X	X	X	X	X	X			BP and pulse rate will be measured after the participant has been resting for 5 minutes.
12-lead ECG	X								Single 12-lead ECG. After the participants has been recumbent for 5 minutes.
ECOG Performance Status (or Lansky scale)	X	X	X	X		X			Within 3 days prior to C1D1. Thereafter, prior to dosing at treatment visits. Lansky scale to be used instead of ECOG in pediatric participants ≤16 years old.

Study Period	Screening Phase	Intervention Phase (Q3W)			End of Treatment	Post-treatment Follow-up			Notes
		1	2	3 and onwards		Safety Follow-up a	Follow-up b	Survival Follow-up	
Treatment Cycle					Discontinuation				Procedures should occur predose on Day 1 of each cycle unless otherwise noted.  Post-treatment Period: Refer to Section 8.12.3.
Scheduled Timing	-28 to -1				At time of d/c	30 days post last dose		~Q12W (telephone)	
Window (days):		+ 3	± 3	± 3		+ 7	± 7	± 7	
AE/SAE Review	X	X	←----->						AEs: monitored up to 30 days after last dose. SAEs and pregnancy: monitored up to 90 and 120 days after last dose, respectively, or 30 days after last dose if participant starts a new anticancer therapy, whichever is sooner.
Laboratory Procedures (LOCAL laboratory)									
Pregnancy Test – Serum or Urine (WOCBP only)	X		X	X	X	X	X		Refer to Appendix 5. Within 72 hours prior to C1D1, then repeat prior to each cycle of treatment and as required by local guidelines up to 120 days after last dose of study intervention or the start of a new anticancer therapy, whichever comes first.
HIV, hepatitis B and C screen (per local regulations)	X								Not required unless mandated by local health authority.
PT/INR and aPTT	X								Within 3 days prior to C1D1. Repeat as needed for participants on warfarin-based anticoagulation therapy.

Study Period	Screening Phase	Intervention Phase (Q3W)			End of Treatment	Post-treatment Follow-up			Notes
		1	2	3 and onwards		Safety Follow-up a	Follow-up b	Survival Follow-up	
Treatment Cycle					Discontinuation				Procedures should occur predose on Day 1 of each cycle unless otherwise noted.  Post-treatment Period: Refer to Section 8.12.3.
Scheduled Timing	-28 to -1				At time of d/c	30 days post last dose		~Q12W (telephone)	
Window (days):		+ 3	± 3	± 3		+ 7	± 7	± 7	
T3 (or Free T3), Free T4, and TSH	X		X	X	X				Within 10 days prior to C1D1. Then within 1 day prior to Day 1 of every other cycle starting from Cycle 2 (eg, Cycle 2, 4, 6, 8, etc.) and at EOT. Free T3 is acceptable where T3 cannot be determined.
Hematology	X		X	X	X	X			Blood for hematology and chemistry panel should be collected within 3 days prior to C1D1 and then within 1 day prior to Day 1 of every cycle. Urine for urinalysis should be collected within 3 days prior to C1D1 and then within 1 day prior to Day 1 of every 4 cycles starting from Cycle 4 (eg, Cycle 4, 8, 12, 16, etc.). Every effort should be made to collect samples at the same time of day.
Chemistry Panel	X		X	X	X	X			
Urinalysis	X			X	X	X			
Laboratory Procedures (CENTRAL laboratory)									
Blood for Future Biomedical Research		X							

AE=adverse event; aPTT=activated partial thromboplastin time; BP=blood pressure; C=Cycle; C1D1=Cycle 1 Day 1; CR=complete response; CT=computed tomography; D=Day; ECG=electrocardiogram; ECI=Event of Clinical Interest; ECOG=Eastern Cooperative Oncology Group; EOT=End of Treatment; HIV=human immunodeficiency virus; INR=international normalized ratio; MRI=magnetic resonance imaging; PD=progressive disease; PT=prothrombin time; Q3W=every 3 weeks; Q12W=every 12 weeks; Q24W=every 24 weeks; RECIST=Response Evaluation Criteria In Solid Tumors; SAE=serious adverse event; SIM=Site Imaging Manual; T3=triiodothyronine; T4=thyroxine; TSH=thyroid stimulating hormone; WOCBP=women of childbearing potential.

- a If the EOT visit occurs  $\geq 30$  days after the last dose of study intervention, a Safety Follow-up Visit is not required. In this situation, all procedures required at the 30-day Safety Visit and EOT are performed once and entered into the EOT visit only.
- b In the Follow-up Phase, participants should be assessed Q12W until Week 54 after C1D1 ( $\pm 7$  days); Q24W thereafter or sooner if clinically indicated, or more frequently if required by local standard of care, until disease progression per RECIST 1.1, to monitor disease status.
- c The same imaging technique regarding modality and the use of contrast should be used in a participant throughout the study to optimize the visualization of existing and new tumor burden. Imaging of any anatomy that shows disease either at Screening or in subsequent evaluations will be required and should be submitted to the imaging contract research organization (iCRO).
- d Participants who attain an investigator-determined CR and stop study intervention with pembrolizumab will have a Safety Follow-up Visit and move to the Follow-up Visits per SoA. Imaging at EOT is not required if the previous tumor imaging assessment was within 4 weeks prior to EOT visit. On-study brain or bone scans should be performed if clinically indicated or to confirm CR (if other lesions indicate CR and brain or bone lesions existed at baseline).

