## 4 STUDY DESIGN

### 4.1 Overall Design

This is a single-arm, open-label, multicenter, efficacy and safety study of pembrolizumab in adult and pediatric patients with previously untreated advanced MCC.

Approximately 50 participants will be enrolled into the study.

Study intervention administration will begin on Day 1 of each 3-week dosing cycle. Study intervention should begin on the day of allocation or as close as possible to the date on which the participant is allocated/assigned.

Participants will have baseline imaging performed at Screening and the first on-study imaging will be done at Week 12 ( $\pm 7$  days) after C1D1. Subsequently, imaging will be performed Q12W ( $\pm 7$  days) or sooner if clinically indicated until Week 54 ( $\pm 7$  days) of study intervention, independent of any treatment delays, Q24W thereafter or sooner if clinically indicated or more frequently if required by local standard of care. Pembrolizumab administration will continue until confirmed PD, unacceptable AE(s), pregnancy, intercurrent illness that prevents further administration of treatment, investigator's decision to discontinue the participant, administrative reasons requiring cessation of treatment, or until the participant has received 35 administrations of pembrolizumab (approximately 2 years). Participants who attain an investigator-determined confirmed CR may consider stopping study intervention after receiving at least 8 study intervention administrations in total and at least 2 additional administrations of study intervention beyond the date when the initial CR was declared.

Participants will be permitted to continue study intervention beyond RECIST 1.1-defined PD as long as the treating investigator considers that the participant may experience clinical benefit with continued treatment, and the participant is tolerating study intervention as per iRECIST. Treatment beyond disease progression per iRECIST may be permitted upon Sponsor consultation and approval.

The primary endpoint of ORR (the proportion of participants with OR) will be assessed by BICR per RECIST 1.1 criteria. Safety and tolerability will be assessed by clinical review of all relevant parameters including AEs, laboratory tests, vital signs, and electrocardiogram

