### **8.2 Efficacy Assessments**

#### **8.2.1 Tumor Imaging and Assessment of Disease**

Throughout this section, the term 'scan' refers to any medical imaging data used to assess tumor burden and may include cross-sectional imaging (such as CT or MRI), medical photography, or other methods as specified in this protocol.

In addition to survival, efficacy will be assessed based on evaluation of scan changes in tumor burden over time, until the participant is discontinued from the study or goes into Survival Follow-up. The process for scan collection and transmission to the iCRO can be found in the Site Imaging Manual (SIM). Tumor scans by CT are strongly preferred. For the abdomen and pelvis, contrast-enhanced MRI may be used when CT with iodinated contrast is contraindicated, or when mandated by local practice. The same scan technique should be used in a participant throughout the study to optimize the reproducibility of the assessment of existing and new tumor burden and improve the accuracy of the response assessment based on scans.

Note: for the purposes of assessing tumor scans, the term “investigator” refers to the local investigator at the site and/or the radiological reviewer at the site or at an offsite facility.

In general, scans should include the chest, abdomen, and pelvis.

Expedited confirmation of measurable disease based on RECIST 1.1 by BICR at Screening will be used to determine participant eligibility. Confirmation by the BICR that the participant's imaging shows at least 1 lesion that is appropriate for selection as a target lesion per RECIST 1.1 is required prior to participant allocation.

All scheduled imaging for all study participants will be submitted to the iCRO. In addition, imaging that is obtained at an unscheduled time point for any reason (including suspicion of progression or other clinical reason) should also be submitted to the iCRO if it shows progression, or if it is used to support a response assessment. All imaging acquired within the protocol-specified window of time around a scheduled imaging visit can be classified as pertaining to that visit. Photographs of cutaneous lesions do not need to be submitted to the iCRO.

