### **8.2.1.2 Tumor Imaging During the Study**

The first on-study scan should be performed at 12 weeks (84 days  $\pm$ 7 days) from the date of allocation. Subsequent tumor scans should be performed every 12 weeks (84 days  $\pm$ 7 days) or more frequently if clinically indicated. After 54 weeks (378 days  $\pm$ 7 days), participants who remain on treatment will have scans performed every 24 weeks (168 days  $\pm$ 7 days). Scan timing should follow calendar days and should not be adjusted for delays in cycle starts. Scans are to be performed until disease progression is identified by the investigator or notification by the Sponsor, or until the start of new anticancer treatment, withdrawal of consent, or death, whichever occurs first.

Objective response should be confirmed by a repeat scan performed at least 4 weeks after the first indication of a response is observed. Participants will then return to the regular scan schedule, starting with the next scheduled time point. Participants who receive additional scans for confirmation do not need to undergo the next scheduled scan if it is fewer than 4 weeks later; scans may resume at the subsequent scheduled time point.

On-study brain or bone scans should be performed if clinically indicated or to confirm CR (if other lesions indicate CR and brain or bone lesions existed at baseline).

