### **8.2.1.3 End-of-Treatment and Follow-up Tumor Imaging**

For participants who discontinue study intervention, tumor imaging should be performed at the time of treatment discontinuation ( $\pm$ 4 week window). If previous imaging was obtained

within 4 weeks prior to the date of discontinuation, then imaging at treatment discontinuation is not mandatory. For participants who discontinue study intervention due to confirmed disease progression, this is the final required tumor imaging if the investigator elects not to implement iRECIST.

For participants who discontinue study intervention without confirmed disease progression, every effort should be made to continue monitoring disease status by tumor imaging using the same imaging schedule used while on treatment (Q12W until Week 54 after C1D1 [ $\pm 7$  days], Q24W thereafter or sooner or more frequently if required by local standard of care, until disease progression per RECIST 1.1) until the start of a new anticancer treatment, disease progression, pregnancy, death, withdrawal of consent, or the end of the study, whichever occurs first.

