#### **8.12.3.2 Follow-up Visits**

Participants who discontinue study intervention for a reason other than disease progression will move into the Follow-up Phase and should be assessed Q12W until Week 54 after C1D1 ( $\pm 7$  days), Q24W thereafter or sooner if clinically indicated or more frequently if required by local standard of care, until disease progression per RECIST 1.1, to monitor disease status. Every effort should be made to collect information regarding disease status until the start of

new anticancer therapy, disease progression, death, end of study. Information regarding poststudy anticancer treatment will be collected if new treatment is initiated. Participants who attain an investigator-determined CR and stop study intervention with pembrolizumab will have a Safety Follow-up Visit and move to follow-up visits per Section 1.3 (SoA).

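### Does the switch from 12-weekly to 24-weekly scans at Week 54, which is not a 12-weekly scan week, leave the two-missed-assessments rule for PFS and DOR unusable?

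*Combined protocol and SAP*

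**What the plan says.** All the imaging text places the change of interval at Week 54. The Schedule of Activities has "Imaging to be performed Q12W or sooner if clinically indicated from the date of C1D1 until Week 54 of study treatment". Section 4.1 continues with "Q24W thereafter or sooner if clinically indicated or more frequently if required by local standard of care". Section 8.2.1.2 says "Subsequent tumor scans should be performed every 12 weeks", marks the switch with the words "After 54 weeks (378 days" and a tolerance of 7 days either way, and adds that "participants who remain on treatment will have scans performed every 24 weeks". For participants off treatment, section 8.2.1.3 keeps "the same imaging schedule used while on treatment" and section 8.12.3.2 says they "should be assessed Q12W until Week 54 after C1D1".

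Week 12 is the only scan week the protocol names. Weeks 24, 36 and 48 follow by adding 12. On allocating scans to visits, section 8.2.1 says "All imaging acquired within the protocol-specified window of time around a scheduled imaging visit can be classified as pertaining to that visit". It does not say how to treat a scan outside every window.

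In the SAP, Table 8 (DOR) and Table 9 (PFS) count a progression or death as an event after at most one missed assessment. After two or more consecutive misses they censor it at the last earlier assessment. The note to Table 8 says what makes an assessment missed. Neither table lists the assessments that are due.

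**The concern.** A rule that counts missed visits needs a list of visits. Here the list is clear up to Week 48 and then depends on a date midway between two scan points. The tolerance attached to Week 54 could suggest a scan at that week, while the 12-week spacing rules one out. The 24 weeks could be counted from Week 48, 54 or 60.

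For a participant with a gap around or after Week 48, the choice can decide whether a late progression counts as an event or is censored months earlier. Section 4.2 rests the study's support for the postmarketing requirement on ORR together with durable responses. The study is open-label, so in principle a list could be settled after data have been seen. It is reasonable to ask whether the durability results could hang on an unstated convention.

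**Working it through.** **1. The plan's own figures.** Section 8.2.1.2 converts weeks to days: 12 × 7 = 84, 24 × 7 = 168, 54 × 7 = 378. All three reproduce. Then 378/84 = 4.5. Week 48 is day 336 and Week 60 is day 420, so Week 54 is 42 days from each and well outside the 7-day windows.

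**2. Which lists fit the text.** Two lists keep every gap at 12 or 24 weeks: 48-72-96 (24 weeks from the last 12-weekly scan before Week 54) and 48-60-84. Two others can be constructed, but each contains an interval found nowhere in the protocol: 48-54-78 has a gap of 54 − 48 = 6 weeks, and 48-78-102 has one of 78 − 48 = 30 weeks. This matters because some striking cases need the irregular lists. Missed counts in the order 48-72-96, 48-54-78, 48-60-84, 48-78-102:

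- Death at Week 82 after a last scan at Week 48: 1, 2, 1, 1. Only 48-54-78 censors it.
- Progression at Week 78 after a last scan at Week 36, strict windows: 2, 2, 2, 1. Only 48-78-102 makes it an event.

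On the two regular lists these cases agree (1 and 1; 2 and 2).

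**3. Where the two regular lists disagree (strict windows).**

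| Last scan | Progression found | Missed on 48-72-96 | Missed on 48-60-84 |
|---|---|---|---|
| Week 36 | Week 72 | 48: event | 48, 60: censored at 36 |
| Week 48 | Week 96 | 72: event | 60, 84: censored at 48 |
| Week 48 | Week 72 | none: event | 60: event |
| Week 36 | Week 78 | 48, 72: censored at 36 | 48, 60: censored at 36 |

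Disagreement covers progression found in Weeks 62 to 73 after a Week 36 scan, and in Weeks 86 to 97 after a Week 48 scan. If a late scan may stand for the preceding due visit, the first two rows have one miss on both lists and the disagreement goes.

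**4. Full attendance.** Anyone who keeps all scans on any of the four lists has a Week 48 scan, and later gaps of at most 30 weeks. No such gap contains two due windows of another list, so no one is reclassified. The enumeration confirms this.

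**5. Size.** Inputs from section 2.2.1.3: 28 responders and 5 with stable disease of 50, so (28 + 5)/50 = 66% taken as progression-free at 2.8 months (about Week 12.2); PFS 52% at 12 months (about Week 52) and 48% at 24 months. Assumed: 10% of scans missed at random.

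- PFS at Week 36 by straight line: 66 − 14 × (36 − 12.2)/(52 − 12.2) = 57.6%.
- Drop from Week 36 to 24 months: 57.6 − 48 = 9.6 points, or 0.096 × 50 = 4.8 participants.
- Each needs one particular scan missed, with at most two such chances: 4.8 × 0.10 = 0.48 to 4.8 × 0.20 = 0.96 participants.

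Simulation agrees. Comparing only the two regular lists gives 0 to 0.5 of 50 with strict windows, and 0 to 0.1 if late scans are credited. Across all four lists with strict windows it is 0.2 to 0.6. With 20% of PFS events taken as deaths, the choice of counting list then moves the 24-month PFS rate by 0.3 to 0.9 points on average, and by up to about 3.5 points in 1 trial of 20. For scale, Table 11 gives 33.7% to 62.6% for 24 of 50, a half-width of (62.6 − 33.7)/2 = 14.45 points.

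**The case for a change.** The strongest opposing case is that the missed-visit rule exists for participants with gaps, so the good behavior of full attenders is no defense. One skipped scan is enough, Table 10 groups DOR with the key secondary endpoints, and in a sample of 50 one late event is visible on the tail of a curve. On an exponential curve with the 16.8-month median the numbers rise: 0 to 1.75 of 50 between the two regular lists with strict windows, and 1.1 to 2.1 across all four.

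The gap stands as a fact, and so does the sensitivity of the tail. The exponential figure carries less weight. It implies 0.5^(12/16.8) = 61% at 12 months and 0.5^(24/16.8) = 37% at 24 months, a fall of 24 points in the second year. Section 2.2.1.3 reports 52% and 48%, a fall of 4. The exponential therefore puts far too many events where the lists can disagree.

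Three other arguments add little:

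- Scan dating by itself makes 18-month PFS differ across the four lists, by about 4 points on the section 2.2.1.3 curve. This comes from dating progression at the detecting scan. It arises with complete attendance and is not a missed-visit problem.
- Examples built on deaths meet a separate inconsistency for PFS: section 9.6.1.3 says any death counts as a progression event, while Table 9 censors a death after two misses. Table 8 has no such sentence, so death examples remain valid for DOR.
- An interval-censored sensitivity analysis would avoid counting visits, but it would leave the main analysis as it is and could not place a median precisely inside a 24-week interval.

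**Conclusion.** No change to the plan follows. This is a missing detail that an analyst fills sensibly. Running the 24 weeks from the last 12-weekly scan before Week 54 gives 12-24-36-48-72-96, keeps every stated interval, and produces sound PFS and DOR estimates. Recording that list and a window convention in the programming specification carries out Tables 8 and 9 without altering their method. Nothing here bears on how often participants ought to be scanned.

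The likely effect is fewer than one participant in 50, and under one point on average in 24-month PFS against a half-width of about 14 points. The study has no hypotheses, and ORR and OS do not depend on the count. These sizes assume 10% of scans missed at random, sites following one list while the count uses another, and a curve like that in section 2.2.1.3. No size was derived for DOR. The Site Imaging Manual and the supplemental SAP, which the protocol cites, were not available and may already list the scan weeks.
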